Distribution	Patient sends prescription to a wholesaler, which then ships the CGM system to the patient. The system consists of a CGM sensor, a transmitter, and a receiver.	
 
Requires that the patient take action to fill prescription
 
	Program houses stock of CGM systems. System is provided to patient along with program materials.	
 
After the consent form is signed, no action required by patient in order to receive device.
 

CGM system set-up and application	Patient applies device in-home, using manufacturer's instruction book, video, and technical assistance by phone.	
 
Technical hurdles of system set-up and device application are especially challenging for seniors.
 
	Program sets up apps and links program devices on behalf of patient before patient receives the system. Resources and instruction will be available in written form, video, telephone, and/or in-person to help patients with device application and system usage.	
 
Minimal system set-up required of patient
 
Expanded, personalized resources are provided to help patient learn to apply device and use system.
 

CGM-based education	Patient learning is self-directed	
 
Benefit of using CGM may be limited by patients' capacity to understand and interpret data, literacy, sense of self-efficacy, or other factors.
 
	Patients receive provider-approved materials and guidance from a coach to help them 1) understand how to interpret CGM data and 2) observe and determine in real-time how diet, medication, exercise, and other lifestyle choices may help them better control their glucose levels. Coaches will be able to view patient glucose data in order to provide support tailored to individual patients' data and circumstances.	
 
Increased likelihood that patients will benefit from using a CGM system.
 

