#### [Integration with patient care](#)

Throughout the program, patients will be instructed to follow their normal care plan as directed by their physicians and as consistent with ADA 2017 standard-of-care guidelines. This includes taking medications as prescribed; engaging in physical activity—especially walking after meals; eating a diet that optimizes glucose control through food choice and timing; responding to hypoglycemia symptoms with a fingerstick and consuming a pre-determined amount of glucose; and monitoring emotional wellness. By providing a continuous graph of each participant's glucose, the CGM system illustrates how the above-described glucose management behaviors impact the participant's glucose.

Should patients in the course of the program experience any health problems associated with the use of their CGM devices, they will be directed to contact the study doctor's clinical research coordinator. The coordinator will assess the severity and relatedness of the event and arrange for appropriate care. Should patients mention a potential study-related health concern to their coach, the coach will actively work to assure the patient speaks with the study doctor, either through a warm transfer or callback.

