## 8. Treatment of Subjects

This program will provide dedicated resources to assure informed consent.

Patients will be instructed to continue to follow the advice of their physicians, including taking prescribed medications.

Patients will sign and date an IRB-approved consent form that indicates that if they are injured from applying or wearing the CGM system or activity tracker in the course of the program that they will receive treatment and that their insurance may be billed. Copays and costs related to injuries from applying or wearing the CGM devices and activity tracker which are not paid for by patient's insurance will be covered by Savvysherpa (Sponsor). Charges for medical care will be based on insurance contracted rates and not mastercharge sheet prices.

Patients with medical concerns related to the study devices will be instructed to contact the study doctor and/or his staff for evaluation. Patients with any other health concerns will be encouraged to see their health providers, or if needed, seek emergency assistance as part of their normal standard of care.

Patients and study staff will be provided with the device manufacturers' technical assistance telephone numbers to report any device-related problems or concerns.

Patients will be provided with a program phone number to call and report other problems or concerns. Patients who need assistance with the application and use of the CGM system can call their coach or be scheduled for an educational class.

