## 9. Assessment of Safety

While the proposed program is essentially educational in nature, every effort will be made to ensure that patients are using their devices properly. Should any concerns about patient safety arise, patients will be directed to see the study doctor or his staff, and if necessary, seek emergency medical assistance.

The Dexcom Continuous Glucose Monitoring System described in this protocol is considered by the Sponsor to be of non-significant risk as it does not meet the definition of a significant risk device per 21 CFR 812.3(m), in that CGM

- (1) Is not intended as an implant and presents a potential for serious risk to the health, safety, or welfare of a subject;
- (2) Is not purported or represented to be for a use in supporting or sustaining human life and presents a potential for serious risk to the health, safety, or welfare of a subject;
- (3) Is not for a use of substantial importance in diagnosing, curing, mitigating, or treating disease, or otherwise preventing impairment of human health and presents a potential for serious risk to the health, safety, or welfare of a subject; or
- (4) Otherwise does not present a potential for serious risk to the health, safety, or welfare of a subject.

Additionally, the system is being used in a manner not entailing significant risk, in that it is being used for educational purposes and as an adjunct to normal care.

The following information supports a non-significant risk determination for the device that will be used in this protocol:

- Chesapeake IRB has previously designated this CGM investigational device as a Non-Significant Risk device for our research protocol Pro00021722;
- FDA-approved Dexcom CGM Systems have been considered a non-significant risk device;
- The CGM devices used in this study are being used on-label in the intended population;
- The Medtronic-Minimed Guardian RT® CGMS, an FDA-approved device using similar technology, has been considered a non-significant risk device;
- The FreeStyle Navigator® CGMS, an FDA-approved device using similar technology, has been considered a non-significant risk device;
- The insertion needle thickness used in the device is not significantly thicker than the needles used in syringes for insulin injection and the potential needle insertion depth is less than 0.6 inches;

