- None of the expected device-related adverse events as defined in the protocol and associated documents would be life-threatening or would result in any permanent impairment of a body function or permanent damage to a body structure;
- There are no expected electrical safety risks as the device has passed the electrical safety tests as per EN45502-1 and EN60601;
- If the subject feels any discomfort during the course of the study, he/she will be able to remove the device immediately (the device is not permanent);
- The device is being used to complement, not replace, self-monitoring of blood glucose meter information, and readings are not intended to be used alone to make diabetes self-management decisions. As with the currently approved device and per intended use of similar technologies, subjects in the study will be instructed not to use the device for diabetes therapy or management;

- Subjects will be instructed to monitor their blood glucose levels as per their usual practice.

Adverse events (AE) associated with the use of the device include pruritus (severe itchiness present 48 hours after removal), erythema (reddening of the skin present 48 hours after removal), and inflammation (swelling and pain, defined as 8 or greater on a 10 point scale 48 hours after removal) where the adhesive touches the skin; local infection at insertion site; and shooting pain located at the site of the sensor (defined as 8 or greater on a 10 point scale). Rarely, the sensor wire will fracture when the sensor is being inserted, worn, or removed. If a sensor breaks and no portion of it is visible above the skin, the participant will be instructed to not remove it and seek medical care from the study doctor and/or his staff.

No serious adverse events (SAE) or Unanticipated Problems (UP) are expected as a result of participation in this minimal risk study. However, AE, SAE and UP will be monitored in the following ways:

- Participants in the study will be instructed to call the study doctor's clinical research coordinator to report all AE, SAE and UP related to the use of the CGM devices. The study doctor and/or his staff will assess the severity of any health problems associated with the device, and if needed, see the patient at the study clinic to assure appropriate care.

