Because the CGM data is an adjunct to patients' diabetes care, the investigator and research staff will NOT constantly monitor patients' realtime CGM data nor will research staff and coaches contact patients' medical providers on behalf of patients when low or high CGM values are observed. Patients will be responsible for using the blood glucose meter to manage their diabetes and to seek medical attention when needed.

Episodes of hyperglycemia or hypoglycemia that require patients to seek medical attention will be considered an AE or SAE depending upon the situation.

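### Section 9 makes medically attended hypo- or hyperglycemia an AE or SAE without stating a device condition, but participants are told to report device-related events and no visible step asks about the rest

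*Combined protocol and SAP*

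**What the plan says.** **The definition.** Section 9 (Assessment of Safety) ends with the rule "Episodes of hyperglycemia or hypoglycemia that require patients to seek medical attention will be considered an AE or SAE depending upon the situation". The trigger is the need for medical attention. The closing phrase bears on whether the event is an AE or an SAE.

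**What participants are told.** Section 9 instructs them to call the study doctor's clinical research coordinator "to report all AE, SAE and UP related to the use of the CGM devices". Section 6 (Integration with patient care) opens its reporting route in similar terms: "Should patients in the course of the program experience any health problems associated with the use of their CGM devices". A second route in that section begins "Should patients mention a potential study-related health concern to their coach". For everything else, Section 8 says: "Patients with any other health concerns will be encouraged to see their health providers, or if needed, seek emergency assistance".

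**Other routes.**
- Coaches call weekly during CGM use (Section 6) and listen for any AE, SAE or unanticipated problem, not only device-related ones (Section 9).
- Coaches remind participants when the Standard of Care guidelines advise seeking medical help for very high, swinging or repeatedly low glucose (Section 9). Figure 1 in Section 6 adds: "Coaches will be able to view patient glucose data".
- Reports reaching the manufacturer's technical support are passed to the Sponsor, and the coordinator follows up (Section 9).
- Section 8 provides a general line: "Patients will be provided with a program phone number to call and report other problems or concerns". Section 9 states: "Should any concerns about patient safety arise, patients will be directed to see the study doctor or his staff".
- Section 7 provides for outreach when device data stop arriving.
- Appendix B lets a coach transfer an unlisted complaint to the clinic.

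**Records and claims.** Section 10 collects these for all participants, including those who stop early. It names use of medical care as an endpoint under Program effectiveness.

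**The concern.** The event definition is wider than the reporting instruction. The definition turns on whether care was needed, while the instruction turns on whether the participant connects the event with the device. Section 6 gives the judgment of relatedness to the coordinator, yet the wording of the instruction leaves the participant to make it first. An episode that the participant sets aside as unrelated may never reach the coordinator.

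What is at stake is the completeness of a safety count that the protocol itself defines. Participants are Medicare Advantage members coached toward better glucose control, and the Section 10 medication list includes basal and bolus insulin, glipizide and glyburide. Section 10 also says that the study is meant to inform a larger one. A low count that rests on volunteered reports could be carried forward as reassurance when it partly reflects that nobody asked.

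**Working it through.** The plan gives no event rate or capture figure on this point, so the check is mainly a comparison of texts.

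**Step 1: follow one case through the instructions.** Suppose a participant is treated in an emergency department for low glucose and does not connect it with the sensor.
- Section 9 definition: the event is an AE or SAE.
- Section 9 instruction to participants: as the participant sees it, the event is not related to the CGM devices, so no call is due.
- Section 6, Integration with patient care: the first route has the same limit, and the second applies only if the participant raises the matter with the coach as possibly study-related.
- Section 8: the participant has already done what is advised for other health concerns. That advice does not ask them to tell the study.

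The event can go unrecorded although every instruction was followed.

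**Step 2: ask whether another route would find it.**
- Weekly coach calls: yes, if the participant mentions the visit. The visible hypoglycemia content is education in self-treatment and reminders about when to seek care, not a question about care already received.
- Coach view of glucose data: this may show a low reading and prompt a conversation, but Section 9 rules out constant real-time monitoring, and a reading does not show that care was sought.
- Manufacturer support, the program phone line and the Appendix B transfer: each needs someone to raise the event.
- Referral of safety concerns to the study doctor: this starts once a concern is known.
- Outreach when data stop: this is triggered by missing data, not by an episode.

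These are real routes, but passive ones for a past visit.

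**Step 3: count the visible prompts.** Appendix B shows scripts for redness or rash, itchiness, site pain, swelling, bruising, bleeding, infection and broken sensor wire. That makes 8, of which 0 concern a glycemic episode. They are triage used after a complaint, so this shows only that the visible scripts supply no prompt.

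**Step 4: check the data-collection table in Section 10.** It has 28 visible rows.
- Cancer and heart-failure indicators are present, at enrollment only.
- Footnote 1 allows abstraction from medical records or claims for 17 rows: age (1) + those two indicators (2) + diabetes-medication indicators (13) + other prescription drugs (1) = 17. Total cost also comes from claims, under footnote 7.
- Rows collected after enrollment that name encounters or glycemic diagnoses: 0.

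**Step 5: check what feeds the AE record.** Section 9 names manufacturer transfers, the study doctor and staff conversations with participants. Records and claims are not named there, and no visible text in Sections 9, 10 or 17 reconciles them with the AE record.

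**Step 6: bound the contact volume for the fix.** 1 call per week × 10 weeks = 10 calls per participant. 10 × 500 participants = 5,000 calls, if all 500 complete the 10 weeks. This measures the effort of the fix, not the size of the problem.

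**The case against.** The strongest reply is that Section 9 describes several routes that work together, and that the coach route covers any AE during weekly contact on exactly this topic. That stands. A reader might infer that these episodes have no way into the AE record, and the documents do not support that. What is missing is active questioning.

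Second, the definition does not say that episodes count regardless of device involvement. It is an unqualified sentence in a section whose listed events are device-associated. This also stands: the text supports only that no device condition is stated.

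Third, much of the relevant material cannot be seen: the consent form, Standard of Care document, full Anticipated Complaints Guidebook, operating procedures, Case Report Form, exit interview and the content of Appendix C. Any of these might hold the missing prompt. A reader might infer that nobody asks anywhere. The documents support only that no visible step does.

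Fourth, the study is exploratory, has no comparison group and names no AE count as an endpoint. That lowers the weight of the point, and such a count could not be attributed to the program in any case. It does not remove the mismatch between definition and instruction.

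**Conclusion.** The mismatch is in the text. Section 9 defines an event more widely than it asks participants to report, and the remaining visible routes generally depend on the event being mentioned. The count of medically attended glycemic episodes may therefore be incomplete. By how much cannot be derived, because the documents give neither an event rate nor a capture fraction.

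A reader might infer that the study holds no diagnosis data, or that claims are used only for cost. Neither is so: the table includes diagnosis indicators at enrollment, and many rows may draw on claims. The narrower statement holds, that no row collected after enrollment names encounters or glycemic diagnoses.

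The conclusion rests on two assumptions: that the unqualified definition means what it says, and that the unseen documents do not already contain the prompt. It is a modest point about safety ascertainment, not about the choice of analysis, and worth correcting because correction is easy.

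**What to change.** 1. Reword the participant instruction in Section 9, and the matching text in Section 6, so that participants also report the glycemic episodes Section 9 defines, whether or not they think the device was involved.
2. Add one scripted question to the existing weekly coach call: *Since our last call, did you need medical care for low or high glucose?* A yes goes to the study doctor's coordinator, who judges relatedness and seriousness.
3. As a secondary step, establish whether the records and claims held for the utilization endpoint contain encounter diagnoses. If they do, list hypo- or hyperglycemia encounters during the 10 weeks for all enrolled participants, including those who stop early. Reconcile the list with the AE record, send unmatched events to the coordinator, and report both counts.

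**Cost.** The first two steps take a change of wording, one question per call and some coordinator time. The cost of the third is uncertain because the structure of the encounter data is not described. Section 6 (Consent) puts the lag of the eligibility claims at two months. If the same lag applies here, reconciliation would complete the final count without speeding up reporting, and step 2 would remain the timely signal. The reported AE count may rise.

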## 10. Data Collection and Statistical Analysis

This study is a formative evaluation to assess the implementation of a program that uses state-of-the-art tools and techniques (e.g. streamlined patient set-up, multi-channel education through coaching, and high-quality, patient-friendly devices) to engage patients in an educational program for CGM-based diabetes management. To do this, we will collect data to measure the degree to which each of the three program elements has been effective.

As an evaluation study, the study is not hypothesis-driven, and involves no statistical analysis plan for hypothesis-testing. Further, as participation will be based on self-selection with no group assignment; there is no sample size calculation. Rather, this study is exploratory in nature.

In this study we anticipate enrolling 500 patients with T2D. Since our primary aim is to perform a formative evaluation of a new program, we plan to collect measures relevant to enrollment and device distribution processes, telephone and secure text messaging with study participants, and any challenges encountered (by both study participants and administrators) in the implementation of the program. We view these measures as benchmarks that will inform future program iterations and quality improvement efforts. We will also investigate whether the program may be more effective for certain subgroups; for example, whether observed differences in program adoption, persistence, behavior change, or changes in diabetes management markers (e.g., estimated glucose values and hemoglobin A1C measurements), vary according to such factors as age, familiarity with technology, educational attainment, or disease progression.

### Data Collection

Since our program achieves its efficacy through education, self-discovery, and the behavior change that results from that education, we will collect data about our ability to connect with and engage participants in the program. Specifically, we will collect data on recruitment efforts (e.g., recruitment rate; patient preferences in setting up their devices (i.e., via self-start, home visit, or in-class); information related to study enrollment (e.g., method and date of enrollment, pre-program survey); and program engagement metrics (e.g., device calibrations, use of companion mobile application, CGM component completion rates). By enrolling in the study, participants consent to the acquisition, review, and analysis of data from their medical records. We will also collect the following data, which will allow us to both evaluate the program as delivered, and to help us tailor future versions of the program to better serve the participants that we enroll:

- Reasons for declining to participate, as given to program personnel at different contact points
- Recordings of coaching calls and introductory training sessions
- Observations from coaches about the most effective calling procedures, behavioral strategies, talking points, and online facilitation techniques
- Time dedicated to device preparation, and to each aspect of the introductory training session
- Total letters sent, and the number returned due to bad addresses
- Recruitment strategies to which each potential participant was exposed
- Total coaching calls attempted and completed per participant, and the durations of those calls
- Suggestions made during coaching calls and during the exit interview about how to improve the program
- Demographic information such as age, education, and social support
- Survey results to assess familiarity with technology such as computers and smartphones, knowledge about nutrition and self-care, and self-efficacy in disease management.

A secondary goal is to evaluate the effectiveness of the program as implemented in this study. On all patients we will collect interstitial glucose levels from the CGM device, activity and other available data from the activity tracking device, any changes in prescription medication use during the normal course of participants' medical care outside of the study, routine lab measures, any changes in mental health (specifically depression), and total costs of medical care before, during, and after the study. Patients will be asked to share information contained in their medical records and claims through December 31, 2027, even if patients stop early from participating in the study.

The following measurements will be collected from study participants:

Data Elements from Participants	Source	Data Collection Time			
		Study Enrollment	During course of study	CGM Completion (10 weeks)	Post-Program through 12/31/27
Age	Medical Record 	X			
Time since diabetes diagnosis	Enrollment Survey 	X			
Race/Ethnicity	Enrollment Survey 	X			
Hemoglobin A1C	Medical Record	X		X	X
Diabetes Distress Questionnaire	Enrollment Survey 	X			
Cancer Indicator	Medical Record 	X			
Heart Failure Indicator	Medical Record 	X			
Diabetes medication indicator	Medical Record 	X		X	X
Metformin indicator	Medical Record 	X		X	X
Glipizide indicator	Medical Record 	X		X	X
Pioglitazone indicator	Medical Record 	X		X	X
Rosiglitazone indicator	Medical Record 	X		X	X
Sitagliptin indicator	Medical Record 	X		X	X
Linagliptin indicator	Medical Record 	X		X	X
Saxagliptin indicator	Medical Record 	X		X	X
Exenatide indicator	Medical Record 	X		X	X
Liraglutide indicator	Medical Record 	X		X	X
Glyburide indicator	Medical Record 	X		X	X
Basal insulin indicator	Medical Record 	X		X	X
Bolus insulin indicator	Medical Record 	X		X	X
Other prescription drug use	Medical Record 	X		X	X
Interstitial glucose levels	CGM device 		X	X	

Contacts with program coaches	Coaching platform 		X	X	X
Interactions with secure texting	Digital app 		X		X
Accelerometer data, including daily steps, distance walked, calories burned, active minutes, hourly activity, walking goal achievement, stationary time; heart rate; sleep stages, duration, and consistency; and any other metrics as available.	Activity tracking device 		X		X
Total cost of medical care during program	Medical Record 				X
WHO-5 Well-Being Index (depression screen)	Pre/post study surveys	X			X
Exit Interview Questionnaire	Post-study survey 				X

These items will be abstracted from the patient's medical record or administrative claims by Savvysherpa research staff

This survey will be mailed to participants or delivered over the phone by a coach or call agents.

Dexcom will securely transfer CGM-based EGV measurements to Savvysherpa.

"Coaching platform" refers to any interactions with human coaches via phone or secure text message.

Savvysherpa will collect patients' use of text messaging.

Savvysherpa will data from activity trackers via participants syncing their activity tracking devices.

Savvysherpa researchers will identify this from participants' administrative medical claims.

This survey will be mailed to participants or delivered over the phone by a coach or call agents.

